6.7 Treatment exposure and compliance

Sequential blood samples will be collected in all patients up to 8 hours post after the first dose administration (Day 1). **Commercially Confidential Information**

In addition, trough samples to assess PK steady-state will be taken at weekly or two-weekly intervals in Part I and Part II of the study, respectively.

Pharmacokinetic parameters (measures of treatment exposure) will be determined in all subjects treated with CDZ173, as detailed in [Section 8.5](#).

Patients will complete a patient diary to ensure compliance in taking study medication and study drug accountability will be performed by study personnel.

6.8 Recommended treatment of adverse events

Medication used to treat AEs must be recorded on the Concomitant medications/Significant non-drug therapies CRF.

Commercially Confidential Information

Commercially Confidential Information

6.9 Concomitant treatment

All prescription medications, over-the-counter drugs and significant non-drug therapies (including physical therapy and blood transfusions) administered or taken within the timeframe defined in the entry criteria prior to the start of the study and during the study, must be recorded on the Concomitant medications/ Significant non-drug therapies section of the CRF.

Medication entries should be specific to trade name, the single dose and unit, the frequency and route of administration, the start and discontinuation date and the reason for therapy.

7 Discontinuation and study completion

7.1 Discontinuation of study treatment

Patients may voluntarily discontinue study treatment for any reason at any time.

The Investigator should discontinue study treatment for a given patient if, on balance, they believe that continuation would be detrimental to the patient's well-being.

Study treatment must be discontinued under any of the following circumstances:

- Patient withdraws consent
- Pregnancy
- The patient experiences a drug-related serious adverse event
- Diarrhea of CTCAE Grade 2 or higher on 3 consecutive days
- Diarrhea of CTCAE Grade 3 or higher
- Diarrhea or abdominal pain with accompanying fever assessed to be related to a gastrointestinal infection

Commercially Confidential Information

The following deviations from the prescribed dose regimen for study treatment:

- More than 10 missed doses in Part I of the study and more than 28 missed doses of study treatment in Part II (cumulative; whether consecutive or otherwise).

Discontinuation of study treatment will be at the discretion of the investigator, under the following circumstances:

- Any protocol deviation or adverse event that results in a significant risk to the patient's safety
- Use of prohibited treatment, see [Section 5.2](#)

The appropriate personnel from the site and Novartis will assess whether study treatment should be discontinued for any patient whose treatment code has been broken inadvertently for any reason.

Patients who discontinued study treatment prematurely will perform an early treatment discontinuation visit (named V104.1) with the assessments marked with a * in the assessment schedule (including imaging), as soon as possible after their treatment discontinuation.

If the premature discontinuation from study treatment happens before the scheduled V104, the patients will be asked to also return at Day 85, and complete the Visit 105 (without further imaging assessments to avoid additional radiation). This will be considered their last Visit.

If on the other hand the premature discontinuation from study treatment happens at or after the scheduled V104, the patients will in addition to the early treatment discontinuation visit be asked to perform the EOS visit 4 weeks after the treatment discontinuation visit. This will be considered their last Visit.

Subjects who discontinue study treatment or who decide they do not wish to participate in the study further should NOT be considered withdrawn from the study UNLESS they withdraw their consent (see [Section 7.3](#)). If they fail to return for these assessments for unknown reasons, every effort (e.g. telephone, e-mail, and letter) should be made to contact them as specified in [Section 7.2.1](#).

7.2 Study completion and post-study treatment

Each patient will be required to complete the study in its entirety, unless consent is withdrawn. All patients completing the study will be offered continuous treatment in the extension study CCDZ173X2201E1. Study completion is defined as when the last patient completes their End of Study visit, or in the event of an early study termination decision, the date of that decision.

Study completion is defined as when the last patient completes 12 weeks treatment and his/her End of Study visit, or the Visit 105 in the case where the patient rolls over to continuous treatment in the CCDZ173X2201E1 study.

At a minimum, patients will be contacted for safety evaluations during the 30 days following completion of treatment, either via the scheduled EOS visit or via the first visits in the CCDZ173X2201E1 study in the cases where patient rolls over directly to this study for continued treatment.

If the patients directly continue treatment in the extension study (CDZ173X2201E1), the safety follow up is not needed as they will be followed up during the Visits in the extension study. Documentation of attempts to contact the patient should be recorded in the source documentation.

7.2.1 Lost to follow-up

For patients whose status is unclear because they fail to appear for study visits without stating an intention to discontinue or withdraw, the Investigator should show "due diligence" by documenting in the source documents steps taken to contact the patient, e.g. dates of telephone calls, registered letters, etc. A patient should not be formally considered lost to follow-up until his/her scheduled end of study visit would have occurred.

7.3 Withdrawal of consent

Subjects may voluntarily withdraw consent to participate in the study for any reason at any time. Withdrawal of consent occurs only when a subject:

- Does not want to participate in the study anymore, and
- Does not allow further collection of personal data

In this situation, the investigator should make a reasonable effort (e.g. telephone, e-mail, letter) to understand the primary reason for the subject's decision to withdraw his/her consent and record this information.

Study treatment must be discontinued and no further assessments conducted, and the data that would have been collected at subsequent visits will be considered missing.

Further attempts to contact the subject are not allowed unless safety findings require communicating or follow-up.

All efforts should be made to complete the assessments prior to study withdrawal. A final evaluation at the time of the subject's study withdrawal should be made as detailed in the assessment table.

Commercially Confidential Information

7.4 Study stopping rules

The study will be put on temporary hold and safety data will be reviewed if any of the following criteria are met and no further enrollment will take place pending a full safety review conducted by the sponsor

- Two or more patients experience a drug-related serious adverse event
- More than two patients in Part I or more than three patients in Part II report CTCAE (current version) Grade 3 or higher adverse events within the same organ class that are considered to be related to study drug
- The sponsor considers that the number and/or severity of adverse events justify discontinuation of the study
- The sponsor requests it (e.g. in the case of pre-clinical safety findings, or issues with the study drug)

7.5 Early study termination

The study can be terminated at any time for any reason by Novartis. Should this be necessary, patients should be seen as soon as possible and treated as a prematurely withdrawn subject. The Investigator may be informed of additional procedures to be followed in order to ensure that adequate consideration is given to the protection of the subject's interests.

The Investigator will be responsible for informing IRBs/IECs of the early termination of the trial.

8 Procedures and assessments

Table 8-1 Assessment schedule Part I

Patients should be seen for all visits on the designated day, with the assessments performed as per schedule, within the allowed “visit/assessment.

Study phase	SCR	BSL	Dose 1 (10 mg)				Dose 2 (30 mg)				Dose 3 (70mg)				EOS		
			1	2	101	102	103	199	201	202	203	299	301	302	303	304	
¹ Visit Numbers	1	2	101	102	103	199			201	202	203	299	301	302	303	304	499
Days	-50 to -2	-1	1	8	15	28			29	36	43	56	57	64	71	84	112
Visit Window s		-3 days*		+/- 1 day	+/- 1 day			+/- 1 day	+/- 1 day	+/- 1 day		+/- 1 day	+/- 1 day	+/- 1 day	+3 days	+/- 2 days	
Written Informed Consent	X																
Inclusion /Exclusion criteria	X	X ²															
Relevant medical History / Current medical conditions	X	X ²															
Demography	CCI		X														
Physical examination	X	X							X				X		X	X	
CCI	X ³	X							X				X		X	X	
Vital signs and body measurements																	
Body height	X																
Body weight	X	X														X	
Body temperature	X	X	X	X	X	X			X	X	X		X	X	X	X	
Blood pressure / Pulse rate ⁴	X	X	X ⁵	X	X			X ⁵	X	X		X ⁵	X	X	X	X	
ECG evaluation (triplicates)	X	X	X ⁵	X	X			X ⁵	X	X		X ⁵	X	X	X	X	
Hematology, Blood chemistry, Urinalysis	X	X	X	X	X			X	X	X		X	X	X	X	X	
CCI			X	X					X				X		X		
			X	X					X				X		X		
PK blood collection					X ⁷	X	X		X ⁷	X	X		X ⁷	X	X	X	
PD blood collection					X	X ⁸	X	X	X ⁸	X	X		X ⁸	X	X	X	
CCI					X	X			X				X		X		
PBMC for functional T cell assay					X											X	
CCI					X											X	
Drug administration record ⁹					X	X	X	X	X	X	X	X	X	X	X	X	
MRI or CT scan					X ¹¹											X ¹²	
SF-36/WPAI-CIQ Questionnaires					X				X				X		X		
Physician/Patients Global assessment					X				X				X		X		
Patient Narratives																X	
Phase/Study completion					X				X				X		X	X ¹⁴	
Comments													As required				
Adverse Events (comment)													As required				
Concomitant meds/Therapies													As required				

Commercially Confidential Information

Table 8-2 Assessment Schedule Part II

Epoch	Screening		Treatment				Follow-up		Notes
Visit name	SCR	BSL	Treatment			EOT	EOS		
¹ Visit Numbers, Core Period	1	2	101	102	103	104	105	199	¹ Visit structure given for internal programming purpose only
Days	-50 to -7	-1	1	15	29	57	85	112	
Visit windows				+/- 3 day	+/- 3 day	+/- 3 day	+/- 3 day	+/- 5 day	
Written Informed Consent	X								Commercially Confidential Information
Inclusion /Exclusion criteria	X	X ²							
Relevant medical History / Current medical conditions	X	X ²							
Demography	CCI	X							
Physical examination*	X	X	X ⁶	X	X	X	X	X	
		X						X	
CCI	S								
	X ⁴	X			X	X	X	X	
	S								
Randomisation			X						
Vital signs and body measurements									
Body height*	X							X	
Body weight*	X	X			X	X	X	X	
Body temperature*	X	X	X	X	X	X	X	X	
Blood pressure / Pulse rate ⁵	X	X	X ⁶	X	X	X	X	X	
ECG evaluation*	X	X	X ⁶	X	X	X	X	X	
Hematology, Blood chemistry, Urinalysis ⁷	X	X	X	X	X	X	X	X	
CCI	S								
		X	X		X	X	X		

Commercially Confidential Information

Footnotes Assessment Schedule Part II

BSL: Baseline, SCR: Screening, EOT: End of treatment, EOS: End of Study, ICF: Informed Consent Form, S: source data only (not to be captures in the eCRF), X for any blood collection unless otherwise mentioned pre-dose is meant.

Patients can roll over for continuous treatment in the open-label CCDZ173X2201E1 extension study, after their EOT visit. For the patients who do not directly roll over to treatment in the extension study (CCDZ173X2201E1) at the EOT visit, the following applies: During the four weeks after the last day of dosing the patients will be followed-up for safety. On Day 112 patients will undergo the EOS visit.

Commercially Confidential Information

8.1 Informed consent procedures

Eligible patients may only be included in the study after providing written (witnessed, where required by law or regulation), IRB/IEC-approved informed consent.

If incapable of doing so, in cases where the patient's representative gives consent, the patient should be informed about the study to the extent possible given his/her understanding. If the patient is capable of doing so, he/she should indicate assent by personally signing and dating the written informed consent document or a separate assent form.

Informed consent must be obtained before conducting any study-specific procedures (i.e. all of the procedures described in the protocol). The process of obtaining informed consent should be documented in the subject source documents.

The date of signing of informed consent (and withdrawal, if later withdrawn) should be documented in the CRF.

Novartis will provide to Investigators a proposed informed consent form that complies with the ICH GCP guideline and regulatory requirements and is considered appropriate for this study. Any changes to the proposed consent form suggested by the Investigator must be agreed to by Novartis before submission to the IRB/IEC.

Commercially Confidential Information

In the event that Novartis wants to perform testing on the samples that are not described in this protocol, additional Institutional Review Board and/or Ethics Committee approval will be obtained.

A copy of the approved version of all consent forms must be provided to the Novartis monitor after IRB/IEC approval.

8.2 Subject demographics/other baseline characteristics

Patient demographics: year of birth, sex, race, predominant ethnicity and relevant medical history/current medical conditions (until date of signature of informed consent) will be recorded in the CRF. Where possible, the diagnoses and not symptoms should be recorded.

All prescription medications, over-the-counter drugs and significant non-drug therapies (including physical therapy and blood transfusions) administered or taken within the timeframe defined in the entry criteria prior to the start of the study must be recorded on the Concomitant medications/ Significant non-drug therapies section of the CRF.

Medication entries should be specific to trade name, the single dose and unit, the frequency and route of administration, the start and discontinuation date and the reason for therapy.

Investigators have the discretion to record abnormal test findings on the medical history CRF whenever in their judgment, the test abnormality occurred prior to the informed consent signature.

Commercially Confidential Information

8.3 Efficacy / Pharmacodynamics

8.3.1 Efficacy

Commercially Confidential Information

8.3.1.1 Imaging with MRI/CT

For the assessment of the impact of CDZ173 on lymphadenopathy, patients will be scanned in an MRI or a CT scanner as based on clinical practice and local regulation. The same imaging modality will be used throughout the study for the same patient.

Commercially Confidential Information

Commercially Confidential Information

In Part I of the study MRI or CT imaging modalities was used in APDS/PASLI patients for a first estimation of the effect size. In Part II clinical efficacy will be assessed. The SPD approach will be used for primary endpoint while more experimental yet accurate 3D measures will be used for secondary endpoint.

For further details on image acquisition and image analysis, see site operations manual/MRI/CT subject scanning guide and imaging review charter, respectively.

8.3.1.2 High Sensitivity C-reactive protein (hsCRP), Lactate dehydrogenase (LDH), beta2 microglobulin, ferritin, fibrinogen and analysis of erythrocyte sedimentation rate

The following parameters will be measured to assess biomarkers reflecting the efficacy of CDZ173 to reduce systemic inflammatory components of APDS/PASLI: High Sensitivity C-reactive protein (hsCRP), Lactate dehydrogenase (LDH) and for Part II additional: beta2 microglobulin, ferritin, fibrinogen and analysis of erythrocyte sedimentation rate.

Commercially Confidential Information

8.3.2 Pharmacodynamic assessments

Pharmacodynamic assessments are specified below, with the methods for assessment and recording specified in the Study Operations Manual. Assessments will be performed/samples collected at the timepoint(s) defined in the [Assessment schedule](#).

8.3.2.1 *Ex vivo* stimulated phosphorylation of Akt in B cells from whole blood

The pharmacodynamic effect of CDZ173 is assessed using *ex vivo* stimulated and unstimulated phosphorylation of Akt in B cells in the Part I of the study. Akt is a direct downstream target of activated PI3Kdelta. Determination of the percentage (%) of CD20+ phospho-Akt positive cells after *ex vivo* stimulation of whole blood is performed by flow cytometry analysis. Unstimulated cells will serve as controls. The stimulation of fresh samples and freezing of stimulated and unstimulated samples are to be performed at the clinical sites.

8.3.3 Patient-Reported Outcome

8.3.3.1 Short form 36 Survey (SF-36)

The purpose of SF-36 in this study is to assess the physical and mental functioning of patients.

The SF-36 is a widely used instrument to measure generic health status. It is a 36-item questionnaire that has proven useful in monitoring generic and specific populations, comparing the relative burden of different diseases, differentiating the health benefits produced by different treatments, and in screening individual patients.

The SF-36 measures the impact of disease on overall quality of life and consists of eight subscales (physical function, pain, general and mental health, vitality, social function, physical and emotional health) which can be aggregated to derive a physical-component summary score and a mental-component summary score

All patient-reported measures should be completed at the center by the latest 3 hours post dose. Completed questionnaires will be reviewed and examined by the Investigator. The Investigator should review not only the responses to the questions in the questionnaires but also for any unsolicited comments written by the patient.

If AEs or SAEs are confirmed then the physician must record the events as per instructions given in [Section 9](#) of the protocol. Investigators should not encourage the patients to change the responses reported in the completed questionnaires.

8.3.3.2 Work Productivity and Activity Impairment (WPAI) plus Classroom Impairment (CIQ) Questionnaire

The WPAI in this study measures the amount of absence or presence and daily activity impairment attributable to APDS/PASLI. As younger patients (age 12 and above) may also be enrolled in the study the WPAI-CIQ version of the questionnaire will be used for all patients as it also measures the amount of absence or presence for school attendance and daily classroom activity impairment attributable to APDS/PASLI.

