2.2 Secondary objective(s)

Objective	Endpoint

 Part II: To assess the effect of CDZ173 on lymphadenopathy (non-index lesions and spleen) 	
 MRI/CT imaging – e.g. 3D volume of index and measurable non-index lesions selected as per the Cheson methodology, and 3D volume and bi-dimensional size of the spleen

 Part I and II: To assess the pharmacokinetics of CDZ173 in patients with APDS/PASLI 	
 Single dose CDZ173 PK parameters (including but not limited to Cmax and AUC) and trough evaluations after multiple dose

 Part I and II: To assess the efficacy of CDZ173 to modify health-related quality of life in patients with APDS/PASLI 	
 SF-36 (Short Form 36) Survey and WPAI-CIQ (Work Productivity Activity Impairment plus Classroom Impairment Questionnaire)

 Part I and II: To assess the efficacy of CDZ173 by the Physician's Global Assessment (PGA) and the Patient's Global Assessment (PtGA) 	
 Visual analogue scales for PGA and PtGA (for Part II the PGA is a key secondary endpoint)

 Part I and II: To assess biomarkers reflecting the efficacy of CDZ173 to reduce systemic inflammatory components of the disease 	
 C reactive protein (CRP), Lactate dehydrogenase (LDH) For Part II additional: beta2 microglobulin, ferritin, fibrinogen and erythrocyte sedimentation rate (ESR)

 Part I and II: To assess the treatment benefit to individual patients 	
 Narratives

 Part II: To assess the safety and tolerability of CDZ173 in patients with APDS/PASLI 	
 All safety parameters, including AEs, physical exam, vital signs, ECG, safety laboratory (hematology, blood chemistry, urinalysis)

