8.3.3.3 Patient Global assessment Questionnaire

The patient's global assessment questionnaire asks patients about their APDS related well-being using 100 mm visual analogue scale (VAS) ranging from "very poor" (0) to "very good" (100).

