8.3.3.4 Physician's Global assessment Questionnaire

In the physician's global assessment questionnaire the Investigator rates the disease activity of their patient using 100 mm VAS ranging from "no disease activity" (0) to "maximal disease activity" (100).

To enhance objectivity, the physician must not be aware of the specific patient's global assessment, when performing his own assessment on that patient.

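### Does the Investigator's review of patient questionnaires undermine the masking of the Physician's Global Assessment?

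*Protocol*

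**What the plan says.** Protocol 8.3.3.1, under the SF-36 heading, contains general instructions for patient-reported outcomes. It sets a deadline: "All patient-reported measures should be completed at the center by the latest 3 hours post dose". It then says "Completed questionnaires will be reviewed and examined by the Investigator", and asks for more than a completeness check: "The Investigator should review not only the responses to the questions in the questionnaires but also for any unsolicited comments written by the patient". The next paragraph of that section deals with recording any adverse events that are confirmed.

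The PtGA is described in 8.3.3.3 as a visual analogue scale filled in by the patient. The PGA is described in 8.3.3.4, where "the Investigator rates the disease activity of their patient using 100 mm VAS". To protect that rating, 8.3.3.4 adds that "the physician must not be aware of the specific patient's global assessment, when performing his own assessment on that patient". SAP 6.2.2 repeats this rule and adds no procedure.

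Protocol 2.2 lists PGA and PtGA under one objective and notes that "for Part II the PGA is a key secondary endpoint". Protocol 11.5.1 and SAP 6.2.4 compare the arms on each scale, two-sided at 5%, with an analysis of covariance at end of treatment and a repeated-measures model over Baseline, Day 29, Day 57 and Day 85. Protocol 6.5 keeps investigator staff blind to treatment.

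**The concern.** The same role has two tasks that seem to pull against each other. The Investigator must read what the patient wrote, including free-text remarks, and must also rate disease activity without knowing the patient's own global score. No visible sentence says which comes first, gives the tasks to different people, or exempts the PtGA from the review. In the Part I schedule (Table 8-1) the two global assessments share a row, which does not help.

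A site that looked through the questionnaires as they were handed in and then completed the PGA would satisfy 8.3.3.1 and break 8.3.3.4. The PGA would then partly echo the PtGA. Agreement between the two scales would be weaker corroboration than it appears, and a patient's expectation or guess about treatment could pass into the physician's rating. For a subjective key secondary endpoint in a trial of about 30 patients, that deserves a check.

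**Working it through.** The plan states no figure on this point, and Protocol 11.7 gives no power for key secondary variables, so the check is mainly a reading of the text.

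**1. Do the instructions collide in time?**

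| Instruction | Who | When |
|---|---|---|
| Complete the patient-reported measures (8.3.3.1) | Patient | Within 3 hours after the dose |
| Review completed questionnaires (8.3.3.1) | Investigator | No time given |
| Rate the PGA (8.3.3.4) | Investigator | No clock time given |
| Be unaware of the PtGA (8.3.3.4, SAP 6.2.2) | Physician rating the PGA | While rating |

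The 3-hour limit governs completion by the patient. It does not say when the Investigator must read the forms. With two tasks at a visit there are two orders:

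- Review first, then rate: the rater knows the PtGA while rating, so 8.3.3.4 is broken.
- Rate first, then review: 8.3.3.1 is met because the review still happens, and 8.3.3.4 is met.

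If the review includes the PtGA and one person does both tasks, only the second order complies with everything. The masking rule therefore fixes the order without stating it.

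**2. How wide is the review?** The review sentence sits under the SF-36 heading, and 8.3.3.3 does not mention Investigator review. The preceding sentence refers to all patient-reported measures and the text uses the plural, so the wider reading is the more natural one. On the narrow reading the PtGA is not reviewed at all and the conflict disappears.

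**3. Is the order really absent?** The visible rows of Table 8-2 stop before any questionnaire or PGA row, and its footnotes are redacted. Protocol 8.3.2 and 8.4 leave the methods for other assessments to an operations manual that is not public. The order can be called not visible, but not missing.

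**4. What could be at stake numerically?** Suppose that, after aligning the scales (0 to 100 runs from very poor to very good on the PtGA, and from no to maximal disease activity on the PGA), independent changes have equal variance and correlation ρ, and that a rater moves a fraction w of the way to the patient's score. Then

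corr = [(1 − w)ρ + w] / √[(1 − w)² + w² + 2ρw(1 − w)].

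With ρ = 0.3, which is assumed:

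- w = 0.2: (0.24 + 0.20) / √(0.64 + 0.04 + 0.096) = 0.44 / 0.881 = 0.50.
- w = 0.4: (0.18 + 0.40) / √(0.36 + 0.16 + 0.144) = 0.58 / 0.815 = 0.71.

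These values show that correlation is sensitive to contamination. They do not show that contamination occurs, since neither ρ nor w comes from the documents.

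Nor is a higher correlation the same as a biased treatment comparison. Under the same mixing, the expected PGA difference between arms is (1 − w) × (true PGA difference) + w × (PtGA difference). If neither scale differs between arms this is zero for every w. A false PGA signal of this kind needs a PtGA difference that the physician's own rating would not share, for example through patients guessing their arm. Knowing a PtGA score does not in itself tell a blinded rater the treatment.

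**The case for a change.** The strongest contrary case is practical. Masking rules that rely on inference are easily broken at busy sites, the sponsor itself wanted the PGA protected, and one sentence stating the order would cost almost nothing. Treatment blinding does not fully answer this, because a blinded rater can still absorb a patient's guess from the score or the written comments.

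Most of that is fair as advice to sites. It does not show a fault in the plan. The protocol already says that the physician must not know the PtGA when rating, so a site that reviews first has committed a deviation from an explicit rule. A further sentence would restate that rule.

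Two extensions of the argument are weaker. Hiding the SF-36 and WPAI-CIQ answers from the rater as well goes beyond the sponsor's rule, which names only the patient's global assessment, and whether it is desirable is open to debate. Stating a same-visit order also leaves one route open: an Investigator who reviewed the Day 29 PtGA has seen it before rating at Day 57. That is a fair observation, but the visible masking rule does not clearly reach earlier scores, and the proposed sentence would not withhold them.

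**Conclusion.** The concern quotes the documents accurately but does not call for a change. The two instructions are compatible, and followed together they give a PGA recorded before the same visit's PtGA is seen. What remains is an operational detail that sites can supply sensibly and that the redacted schedule or the Site Operations Manual may already contain. Making the order explicit, and saying whether earlier PtGA values are withheld from the rater, would be optional clarifications.

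The size of any effect cannot be derived from the documents. The correlations of 0.50 and 0.71 depend wholly on assumed inputs and show no bias in the treatment contrast. The co-primary endpoints, index-lesion SPD and percentage of naïve B cells, are unaffected.

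The conclusion rests on reading the masking rule as binding at each rating, and on the absence of any hidden instruction requiring the review to come first. If the manual did require that, the two texts would conflict and would need to be reconciled.
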